Primary Hypothesis: In patients with moderate to severe CKD not requiring dialysis (estimated glomerular filtration rate 15-45 ml/min/1.73m²) with absolute iron deficiency (serum ferritin ≤300ng/ml and TSAT ≤ 30%), treatment with ferric citrate will lead to greater improvements in markers of iron bioavailability (serum iron, ferritin, transferrin saturation) than treatment with ferrous sulfate.

Secondary Hypotheses: In patients with moderate to severe CKD not requiring dialysis (estimated glomerular filtration rate 15-45 ml/min/1.73m²) with absolute iron deficiency (serum ferritin ≤300ng/ml and TSAT ≤ 30%), as compared to treatment with ferrous sulfate for 12 weeks, treatment with ferric citrate for twelve weeks will result in (1) a greater rise in hemoglobin concentrations and (2) a lower rise in serum hepcidin concentrations.

3 Investigational Plan (Figure)

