4.1 Primary outcome

The primary outcome variables for this analysis will be transferrin saturation (TSAT) and ferritin concentrations.

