4.3 Statistical Plan

To compare the baseline characteristics between the two groups, student's t-test or chi square test will be used for parametric and non-parametric variables respectively. Subjects' baseline values will serve as the reference for comparison with changes post-intervention. Longitudinal changes in the primary outcome variables will be examined using repeated measures linear mixed models. In these models, time and treatment group will be the fixed variables and participants will be modeled as random terms. We will first test for a time by treatment group interaction to determine whether the change in the outcome variables over time differs by treatment group assignment. If we detect a statistically significant interaction, we will stratify the analysis by treatment group and test the main effect of time in stratified models. If we do not detect a significant interaction, we will remove the interaction term from the model and will test for the main effects of time and treatment group. If we find any differences in baseline characteristics despite randomization, we will adjust for these covariates in secondary models. We will analyze data using an intention-to-treat principle such that all randomized participants who received at least one dose of study medication and had at least one post-baseline assessment will be included to assess efficacy.

4.4 Sample Size Calculation:

The sample size estimation is powered to detect a significant difference in the change in ferritin in response to oral ferric citrate vs ferrous sulfate challenge. In a prior study, treatment with ferric citrate for 12 weeks raised serum ferritin by 77.5 [95%CI 56.2-98.7] as compared to placebo. To detect as small as a 20% lower rise in ferritin in individuals taking ferrous sulfate vs. ferric citrate over a similar period of intervention, we would need recruit 60 individuals overall (30 per arm) assuming a type I error of 0.05 and a power of 80%. This will also provide ample power to detect at least a 20% difference in the change in TSAT as well. While we also plan on examining changes in hepcidin in this protocol, we did not specifically power the analysis for this outcome variable as it is a secondary outcome.

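### Section 4.3 gives each of two primary outcomes a test and a fallback test, with no deciding rule and no named 12-week contrast, so the 0.05 in section 4.4 is not secured

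*Combined protocol and SAP*

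**What the plan says.** Section 4.1 names two primary outcomes without ordering or linking them: "The primary outcome variables for this analysis will be transferrin saturation (TSAT) and ferritin concentrations". The primary hypothesis in section 2 lists three markers: "greater improvements in markers of iron bioavailability (serum iron, ferritin, transferrin saturation) than treatment with ferrous sulfate". Section 3.4.3 lists iron, TIBC and ferritin as primary outcome variables.

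In section 4.3, "time and treatment group will be the fixed variables and participants will be modeled as random terms". The interaction is tested first, to learn "whether the change in the outcome variables over time differs by treatment group assignment". The next step depends on the result:

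- Significant: "we will stratify the analysis by treatment group and test the main effect of time in stratified models".
- Not significant: "If we do not detect a significant interaction, we will remove the interaction term from the model and will test for the main effects", meaning those of time and treatment group.

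The same section makes each participant's baseline the reference for post-intervention change. It does not say whether time is categorical or linear, and it gives no covariance beyond the participant random term.

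Section 4.4 says the study is "powered to detect a significant difference in the change in ferritin in response to oral ferric citrate vs ferrous sulfate challenge". It takes its effect from a 12-week prior result and states the size thus: "over a similar period of intervention, we would need recruit 60 individuals overall (30 per arm) assuming a type I error of 0.05", with 80% power. The 0.05 appears nowhere else.

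**The concern.** The interaction is a between-arm test of efficacy. The group main effect in the reduced model is another between-arm test of the same outcome. Two outcomes with two steps give up to four chances to declare a difference, and the plan does not say which of them makes the trial positive.

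The plan also lacks a named result. A significant interaction over categorical visits says that the arms differ somewhere, not by how much at 12 weeks. The plan follows it only with tests of time within each arm, which compare an arm with itself. If the interaction is not significant, the group effect averages over visits, including early ones where the difference may be small. Neither branch names the quantity that section 4.4 sizes on.

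**Working it through.** **The plan's own figure.** The ferritin effect is 20% of 77.5 = 15.5. Two-sided at 0.05 with 80% power, n per arm = 2 × (1.960 + 0.842)² × (SD/15.5)². Section 4.4 gives no SD. Thirty per arm needs an SD of about 21. The half-width of the quoted interval, (98.7 − 56.2)/2 = 21.25, used as an SD returns exactly 30. Read as a confidence interval, it gives SE = 42.5/3.92 = 10.84. With 72 per arm (72 treated, from section 3.9.1.1; equal arms assumed), SD = 10.84 × √(72/2) ≈ 65 and n = 277 per arm. That is a separate issue. It matters here only because power quoted at SD 21 is back-solved from n = 30.

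**Inputs for the error rate.** From the plan: two outcomes, two steps, 30 per arm, visits at 0, 2, 6 and 12 weeks. Assumed: 0.05 two-sided per test, complete data, compound symmetry (within-person correlation 0.5 to 0.8), outcome correlation 0 to 0.7. Counted: the interaction and group tests only; the time tests are not between-arm tests.

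**Arithmetic and simulation.** Under compound symmetry the interaction uses within-person contrasts and the group test uses person means, so the two are close to independent. Simulated ranges cover categorical and linear time, with baseline as a response row or as change scores.

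| What counts as success | Independent outcomes | Simulated, correlation 0 to 0.7 |
|---|---|---|
| Interaction only, one outcome | 5% | 4.8-5.3% |
| Interaction only, either outcome | 1 − 0.95² = 9.75% | 8.2-10.1% |
| Either step, one outcome | 0.05 + 0.95 × 0.05 = 9.75% | 9.5-10.2% |
| Either step, either outcome | 1 − 0.95⁴ = 18.5% | 15.6-19.0% |
| Either step, both outcomes, neither differs | 0.0975² = 0.95% | 0.9-3.6% |
| Either step, both outcomes, one with a large true effect | 1 × 0.0975 = 9.75% | 9.5-9.9% |

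At outcome correlation 0.9, the second, fourth and fifth rows become about 7%, 13-14% and 6%. If serum iron joins the family, as in section 2, either step on any of three independent outcomes gives 1 − 0.95⁶ = 26.5%.

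**Covariance and time coding.** A random-intercept model was fitted to data with AR(1), random-slope or growing-variance errors. Either step on one outcome gave 9.2-11.5% with categorical time and 12.4-20.1% with linear time. Either step on either outcome gave 15.3-21.8% and 20.5-35.7%.

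**What the fallback estimates.** As a share of the week-12 difference:

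- Baseline as a response row: mean of (0, 2/12, 6/12, 1) = 42% under linear growth; mean of (0, 1, 1, 1) = 75% if constant from week 2. That is 6.5 to 11.6 of 15.5.
- Change scores: mean of (2/12, 6/12, 1) = 56%, or 100%. That is 8.6 to 15.5 of 15.5.

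The sentence making baseline the reference supports the second reading. How often the fallback is reached depends on the SD that the plan does not give.

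**The case against.** The strongest defence is that the interaction is the efficacy test. Section 4.3 gives it the study question, and the later steps can be read as description. With categorical time and baseline as reference, the fitted interaction terms even contain the week-12 difference in change. Most of this stands: on that reading each outcome is tested at 5%. Two outcomes with no success rule still give 8-10%, the plan does not say that the fallback is excluded, and it does not name the week-12 term as the result.

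Three stronger readings are tempting, and the documents do not support them.

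- A reader might infer that the trial's false-positive rate is 16-19%. That is the rate only if either step on either outcome counts, which the plan neither states nor excludes. The 20.5-35.7% range further needs linear time and a misspecified covariance.
- A reader might infer that requiring both outcomes is a safe, conservative reading at 1-4%. That holds only when neither outcome differs. While the fallback remains, a true effect on one outcome leaves about 10% error on the other.
- A reader might infer that the two-step rule has low power. No such claim is made: it can have more power than a week-12 contrast when the effect is constant from week 2, partly because it spends about 10% error per outcome.

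It is also fair that iron and TIBC in section 3.4.3 may simply be the parts of TSAT. That does not explain serum iron listed beside TSAT in section 2. The primary hypothesis names no time point, so week 12 is a proposal drawn from section 4.4.

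**Conclusion.** The concern holds as a gap in the decision rule and in the reported contrast. The 0.05 in section 4.4 is met for a single outcome judged on the interaction alone. It is exceeded if either outcome may succeed (8-10%), if either step may count (about 10% for one outcome), or both (16-19%). A both-must-succeed rule does not hold 5% unless the fallback is removed. These figures rest on 0.05 per test, complete data, compound symmetry and outcome correlation 0 to 0.7, none of which the plan states except the 0.05. Other error structures raise the rates somewhat with categorical time and more with linear time. No between-arm estimate of 12-week change is named on either branch. This should be fixed before analysis.

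**What to change.** First reconcile the primary-outcome lists in sections 2, 3.4.3 and 4.1. Then:

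- **Contrast.** For each primary outcome, make the arm difference in change from baseline at week 12, with 95% CI, the single deciding result.
- **Model.** Use a baseline-adjusted mixed model with categorical visit, treatment-by-visit kept whatever its p-value, unstructured covariance and Kenward-Roger degrees of freedom. These details matter. In null simulations with random-slope or growing-variance errors, a homogeneous AR(1) model rejected at week 12 in 13.5% and 14.9% of trials, and an unstructured model with a Wald z test in about 5.6-6.9%. With complete data, a week-12 ANCOVA on baseline is a simple equivalent check.
- **Two outcomes.** Use a fixed order (ferritin, which section 4.4 sizes on, then TSAT), Hochberg, or a statement that both must succeed on this one contrast. With the week-12 ANCOVA, fixed order gave 4.7-5.3% and Hochberg 4.2-5.2% under every covariance tried. Requiring both is at most about 5%.
- **The rest.** Make the within-arm time tests and the visit-averaged group effect descriptive. If an all-visit comparison is intended, name that one test and drop the fallback.

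The cost is analysis wording, with the same data. Under a fixed order a TSAT claim is lost if ferritin fails. Hochberg or requiring both lowers power somewhat. A week-12 contrast uses less of the data if the effect is constant from week 2. The trade-off should not be judged at an SD of about 21 alone: at SD 65 under compound symmetry, power is about 15-18% for the week-12 ANCOVA and 16-26% for the two-step rule, low for both.

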3.4.3 Visit 1 (Day zero)

After eligibility is confirmed in the screening visit and following the washout period if necessary, participants will come to the UAB Clinical Research Unit (CRU) in the morning after an overnight fast for visit 1 (Day 0). During this visit, participants will undergo fasting blood collection to

establish baseline measurements for primary outcome variables (iron, TIBC, ferritin), secondary outcome variables (hemoglobin, hepcidin, FGF23) and safety measures (eGFR, calcium, phosphorus). At this time subjects will also be randomly assigned to a treatment arm (ferric citrate vs. ferrous sulfate).

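### Secondary-model covariates are chosen by chance baseline differences, and the primary model does not adjust for the Day 0 outcome value

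*Combined protocol and SAP*

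**What the plan says.** Section 4.3 of the combined protocol and SAP covers four things that bear on this point.

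- **Baseline comparison.** The arms are compared at baseline by significance test: "student's t-test or chi square test will be used for parametric and non-parametric variables respectively".
- **Covariates.** "If we find any differences in baseline characteristics despite randomization, we will adjust for these covariates in secondary models". No list of covariates, p-value threshold or size of imbalance is given.
- **Role of the baseline outcome.** Participants' "baseline values will serve as the reference for comparison with changes post-intervention".
- **Primary model.** "In these models, time and treatment group will be the fixed variables and participants will be modeled as random terms". The time-by-treatment interaction is tested first. If it is not significant, it is dropped and the main effects of time and treatment are tested.

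The values needed for adjustment are already collected. Section 3.4.3 has the Day 0 blood draw "establish baseline measurements for primary outcome variables (iron, TIBC, ferritin), secondary outcome variables (hemoglobin, hepcidin, FGF23) and safety measures (eGFR, calcium, phosphorus"). Section 3.4.3.1 describes 1:1 randomisation and mentions no stratification.

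**The concern.** There are two linked problems.

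**The trigger.** In a randomised trial a baseline difference between arms is chance. A test for one says nothing about whether the variable predicts ferritin or TSAT. A strong predictor that happens to be balanced stays out, and an irrelevant variable that happens to differ goes in. With no threshold written, what counts as a difference is settled after the data are seen, in an open-label trial.

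**The primary model.** The Day 0 value of the outcome is likely to be among its best predictors, yet it is not a planned covariate. Used only as the reference for change, it is subtracted with a fixed weight of one, not with the weight the data support. At 30 per arm this can cost precision, and part of any chance baseline gap is carried into the treatment estimate.

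**Working it through.** **Inputs.** From section 4.4: 30 per arm, alpha 0.05 (taken as two-sided), 80% power, and a target ferritin difference of 20% of 77.5 = 15.5. From section 4.2: hepcidin measured in a subset of 30. Not in the documents, so assumed: the baseline-to-follow-up correlation r and the ratio k of follow-up SD to baseline SD.

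**Plan's own figure.** The plan states no figure for baseline adjustment. The only power statement with both effect and SD is for hemoglobin: 0.4 / (0.7 × √(2/30)) = 2.213, and Φ(2.213 − 1.960) = 0.60. The stated value of about 60% is reproduced.

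**Step 1: what the primary contrast is.** I take baseline as one level of a categorical time factor, with a random participant intercept and complete data. The week 12 interaction contrast then equals the between-arm difference in mean change. A mixed-model fit to one simulated data set gave 0.09496 by both routes.

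**Step 2: precision.** In units of baseline variance, the variance of change is 1 + k² − 2rk and the variance after baseline adjustment is k²(1 − r²). The ratio of adjusted to change is k²(1 − r²) / (1 + k² − 2rk), which is (1 + r)/2 when k = 1.

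| r | Ratio, k = 1 | Gain, k = 1 | Ratio, k = 1.25 | Gain, k = 1.25 |
|---|---|---|---|---|
| 0.5 | 0.75 | 25% | 1.172/1.313 = 0.89 | 11% |
| 0.7 | 0.85 | 15% | 0.797/0.813 = 0.98 | 2% |
| 0.8 | 0.90 | 10% | 0.5625/0.5625 = 1.00 | 0% |
| 0.9 | 0.95 | 5% | 0.297/0.3125 = 0.95 | 5% |

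These are large-sample ratios. In 20,000 simulated trials of 30 per arm with k = 1, the ratios were 0.77 at r = 0.5 and 0.87 at r = 0.7, because the slope must be estimated. That takes about two percentage points off the gain.

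At k = 1 and r = 0.5, 0.7, 0.8 and 0.9, the N matching the precision of 60 is 45, 51, 54 and 57. A nominal 80% power becomes 90%, 86%, 84% and 82%. If the hemoglobin SD of 0.7 is a change-score SD and the same analysis were used, 60% would become 72%, 67%, 65% and 62%.

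**Step 3: chance imbalance.** Let d be the observed baseline gap and δ the true effect, with k = 1. The expected follow-up gap is δ + rd, so the change contrast is δ + (r − 1)d. For ferritin, assume a baseline SD of 50 to 90. The standard error of d is then SD × √(2/30), or 13 to 23, about the size of the 15.5 target. With d = 20 and r = 0.7 the shift is −6, and 6/15.5 = 39% of the target.

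After the interaction is dropped, the treatment main effect is the average gap over four visits. If δ is constant after baseline and all visits share the same r, this is [d + 3(δ + rd)]/4 = 0.75δ + d(1 + 3r)/4. With d = 20 the shift is 12.5 at r = 0.5 and 18.5 at r = 0.9. Here the baseline gap enters directly.

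**Step 4: how often the trigger fires.** Sections 3.4.1 and 3.4.3 name 14 characteristics: age, gender, race/ethnicity, height, weight and nine laboratory values. With independent tests at 0.05, both assumed, 1 − 0.95¹⁴ = 51%. Without hepcidin, given the subset, 1 − 0.95¹³ = 49%. The characteristics are correlated, so the true figure is probably somewhat lower.

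**The case against.** The strongest reply is that the rule is confined to secondary models. A reader might infer that the primary analysis depends on data-driven covariates, or that its type I error is inflated. The text does not support that: the main model's terms are set in advance. The trigger frequency in step 4 is only the chance that an extra secondary model is run. It is not an error rate.

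A reader might also infer that baseline values are thrown away. They are not, since they are the reference for change. At k = 1, change from baseline has 2(1 − r) times the variance of an analysis that ignores baseline, which is 0.6 at r = 0.7. The loss is only relative to baseline adjustment.

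The size of that loss is also open to challenge. It rests on r and k, and ferritin is expected to rise, so its spread may rise too. At k = 1.25 the gain nearly vanishes around r = 0.7 to 0.8. This objection stands and is why a range is given.

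On the test wording, the authors probably meant continuous versus categorical. That a skewed laboratory value would go to a chi-square test is an inference from the literal text, and the effect stops at the baseline table and the secondary-model trigger.

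Two things survive. Covariates are still selected by chance differences under a rule with no threshold, and the primary model still leaves baseline imbalance in its estimates.

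**Conclusion.** The point holds as a specification weakness with a free remedy. The difference-triggered rule is a poor way to choose covariates, but it reaches secondary models only. The primary model is pre-specified but makes less than full use of the Day 0 outcome.

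The large-sample variance gain from adjustment is 5% to 25% for r from 0.9 down to 0.5 with equal SDs. It is about 11%, 2% and 0% at r = 0.5, 0.7 and 0.8 if the follow-up SD is 1.25 times baseline. Both sets of figures rest on assumed values and on baseline being a repeated time point, which section 4.3 implies but does not state.

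The imbalance shifts in step 3 are conditional on the observed gap and average to zero over randomisations. They are a matter of precision and credibility in a trial of 60, not of systematic bias. No stated sample size or power figure is shown to be wrong by this point.

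**What to change.** Change section 4.3 as follows.

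1. **Primary model for TSAT and ferritin.** Choose one form in advance and use it whatever the observed balance:
   - keep baseline in the response vector and constrain the baseline means to be equal across arms; or
   - model weeks 2, 6 and 12 only, with the Day 0 value as a covariate.

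   Do not enter baseline both as a response and as a covariate. In the constrained form the treatment effect sits in the treatment-by-visit terms, so the step that drops a non-significant interaction must be reworded.
2. **Secondary models.** Delete the difference-triggered rule. Name any covariates beforehand on prognostic grounds. Baseline eGFR is one example, since section 3.3 ties it to the severity of iron deficiency and to FGF23.
3. **Baseline table.** Describe the arms without significance tests. If tests are kept, correct the wording: a rank-sum test for skewed continuous variables, and chi-square or Fisher for categorical ones.

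The cost is SAP wording only. Every value needed is already collected at screening or Day 0, so no visit, sample or participant is added.

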3.1 General overview

- Randomized, open-label study of ferric citrate vs. ferrous sulfate in patients with moderate to severe CKD (eGFR 15 – 45 ml/min/1.73m²).
- Participants will be recruited from the outpatient nephrology clinics at the University of Alabama at Birmingham (UAB).
- Written informed consent will be obtained at the screening visit after the study has been explained in full.
- Participants taking oral iron supplements at the time of the screening visit will undergo a four week wash-out period prior to beginning study medications.
- After eligibility is confirmed following the screening visit (and wash-out period if necessary), participants will be randomly assigned 1:1 to take ferric citrate at a dose of 2 grams three times a day with meals (n=30) or ferrous sulfate at a dose of 325 mg by mouth three times a day between meals (n=30) for a total of twelve weeks.
- Fasting blood and urine samples will be collected at baseline and two, six and 12 weeks after baseline for measurement of study outcome variables. Data for the outcome variables as well as safety will be collected at these time points.
- The study will end at 12 weeks, a final blood and urine sample will be drawn and intervention will be stopped.

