3.4.4 Visit 2 (week 2)

- Participants will come to the UAB CRU, where participants will undergo vital sign measurement and fasting blood collection for measurement of study outcome variables and safety measures.
- Pills remaining in the study medication bottles of each participant will be counted to ensure compliance and accountability for discrepancies in study drug use will be performed.
- Participants will be asked questions about intercurrent medical events and changes in clinical condition from the last visit. Events that meet the definition of an adverse event (see section 3.9.2) will be documented.

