3.7.2 Discontinuation from the study

Participants can be withdrawn from the study at any time if they specifically ask to withdraw or if, in the opinion of the study PI, continuation of the study would be harmful to the participant. In addition, a participant can be withdrawn at any time by the PI if he or she repeatedly violates study protocol.

Participants withdrawn prior to the final scheduled visit will be asked to attend a close-out visit in which they provide blood and urine samples (for final analyses), and complete documentation related to the development of any adverse events.

If the withdrawal is due to an adverse event, participants will be followed until the event resolves or it is shown that the adverse event was not due to the study medication.

Randomized participants who withdraw prematurely will not be replaced. A participant who withdraws after signing informed consent but before randomization can be replaced.

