Elevated iron concentrations: Increases in markers of iron metabolism are anticipated in participants taking either oral ferrous sulfate or ferric citrate. In order to ensure that iron marker concentrations do not increase too high during the course of intervention, both iron saturation (TSAT) and ferritin will be monitored throughout the intervention period. If TSAT rises above 65% or ferritin rises above 1000 ng/ml at any time point the lab results will be repeated within 48 hours. If the results remain elevated, the participant will be asked to stop the study medication but will continue to be followed for the duration of the study visits.

Gastrointestinal upset: It is possible that study participants can develop gastrointestinal upset (dyspepsia, constipation, diarrhea) during the study duration. If this occurs, the following will happen:

- If the participant was randomized to the ferrous sulfate arm, he or she will be asked to reduce the dose of ferrous sulfate to twice a day. If one week after this reduction he or she continues to experience gastrointestinal upset, he or she will be asked to reduce the dose of ferrous sulfate to once a day. If one week after this reduction he or she continues to experience gastrointestinal upset, he or she will be withdrawn from the study.
- If the participant was randomized to the ferric citrate arm, they will be asked to reduce the dose of ferric citrate to 1 gram by mouth three times a day with meals. If he or she continues to experience gastrointestinal upset one week after they make this change, he or she will be withdrawn from the study.

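### The efficacy set called intention-to-treat is a modified ITT set, and where no close-out sample is obtained its exclusions may differ by arm

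*Combined protocol and SAP*

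**What the plan says.** Section 4.3 announces an intention-to-treat principle and in the same sentence gives the rule for the efficacy analysis: "all randomized participants who received at least one dose of study medication and had at least one post-baseline assessment will be included".

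The first chance to obtain a post-baseline value is week 2. Section 3.1 states: "Fasting blood and urine samples will be collected at baseline and two, six and 12 weeks after baseline". Section 3.4.4 confirms that the week-2 visit includes "fasting blood collection for measurement of study outcome variables and safety measures".

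Section 3.9.1.1 sets different steps by arm for gastrointestinal upset:

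- Ferrous sulfate: first, "he or she will be asked to reduce the dose of ferrous sulfate to twice a day". If the upset persists a week later, "he or she will be asked to reduce the dose of ferrous sulfate to once a day". Withdrawal from the study follows only if it persists for a further week.
- Ferric citrate: there is one dose reduction, and if the participant "continues to experience gastrointestinal upset one week after they make this change, he or she will be withdrawn from the study".

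Section 3.7.2 applies to both arms. It provides another way out: "Participants can be withdrawn from the study at any time if they specifically ask to withdraw". The investigator may also withdraw a participant for harm or for repeated violations. It also provides a partial safeguard: "Participants withdrawn prior to the final scheduled visit will be asked to attend a close-out visit in which they provide blood and urine samples". Randomised participants who withdraw are not replaced.

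Section 3.7.1 expects those who stop study drug to stay in follow-up and complete their visits. Section 4 gives no dropout rate, no missing-data method and no sensitivity analysis, and does not mention the close-out sample.

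**The concern.** Taking a dose and providing a post-baseline value both happen after randomisation, and participants and staff know the assigned treatment. A set that depends on them no longer has the full protection of randomisation, and its label suggests that it does.

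The point has more weight here because one protocol-defined route out of the trial runs on a different clock in each arm. Under the gastrointestinal steps, a ferric citrate participant who is intolerant early can be withdrawn before the first scheduled outcome sample. A ferrous sulfate participant with the same onset cannot. If no later sample is obtained, the first leaves the efficacy set and the second stays in it. If early intolerant participants gain less iron than the rest, their removal from one arm raises that arm's mean rise. With 30 per arm, each participant is 1/30 of the arm.

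**Working it through.** **Yardstick.** Section 4.4 cites a ferritin rise of 77.5 (95% CI 56.2 to 98.7) against placebo and sizes the trial for a 20% lower rise on ferrous sulfate. The target difference is 0.20 × 77.5 = 15.5, taken here as ng/ml, the unit used in the eligibility criteria. The plan's 30 per arm is reproduced at two-sided 0.05 and 80% power if the SD is the CI half-width, (98.7 − 56.2)/2 = 21.25: n = 2 × (1.96 + 0.84)² × 21.25² / 15.5² = 29.4 to 29.5 depending on rounding, so 30. Whether 21.25 is a suitable SD is a separate matter and does not enter below.

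**Timing.** Inputs are the steps in Section 3.9.1.1 and the day-14 visit in Section 3.1 (no visit window is given). Earliest withdrawal is onset + 7 days on ferric citrate and onset + 7 + 7 = onset + 14 days on ferrous sulfate.

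| Onset of upset (day) | Ferric citrate, earliest withdrawal | Ferrous sulfate, earliest withdrawal |
|---|---|---|
| 0 | 7 | 14 |
| 3 | 10 | 17 |
| 6 | 13 | 20 |
| 7 | 14 | 21 |

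Onset on days 0 to 6 therefore gives days 7 to 13 on ferric citrate, before the week-2 sample, and days 14 to 20 on ferrous sulfate, at or after it. The participant leaves the efficacy set only if the close-out sample is also missing or is not counted.

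**Illustrative size, one arm.** Let k of 30 be excluded, with mean rise r × 77.5, and let those retained average 77.5. The shift is the retained mean minus the mean over all 30, which is (k/30) × 77.5 × (1 − r). The documents give neither k nor r, so both are assumptions. The 77.5 is a difference from placebo, used here as a stand-in for an arm mean.

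| k | r = 0 | r = 0.5 | r = 1 | r = 1.25 |
|---|---|---|---|---|
| 1 | 2.58 | 1.29 | 0 | −0.65 |
| 2 | 5.17 | 2.58 | 0 | −1.29 |
| 3 | 7.75 | 3.88 | 0 | −1.94 |

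**Illustrative size, both arms.** Losses can also occur on ferrous sulfate. Take retained rises of 77.5 and 0.80 × 77.5 = 62, with no rise in those excluded. The net shift toward ferric citrate is 77.5 × kF/30 − 62 × kS/30, where kF and kS are the numbers excluded on ferric citrate and ferrous sulfate:

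- kF = 2, kS = 2: 5.17 − 4.13 = 1.03 (from unrounded terms)
- kF = 3, kS = 1: 7.75 − 2.07 = 5.68
- kF = 2, kS = 3: 5.17 − 6.20 = −1.03

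**Would keeping baseline-only records be enough?** No. Take one baseline and one follow-up value, and let b be the slope of follow-up on baseline. Adding baseline-only participants to a likelihood model changes the estimated mean change by −(1 − b) × (baseline mean of all − baseline mean of those retained). The unseen rise does not appear in this expression. If those lost had similar baselines, the estimate hardly moves. A stated assumption about the missing values is needed.

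**The case against.** A reader might infer that only ferric citrate participants can be lost before week 2. The documents do not support that. The asymmetry belongs to the gastrointestinal steps alone. Under Section 3.7.2 a ferrous sulfate participant who is intolerant in the first days can simply ask to leave.

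A reader might also infer that the comparison is biased toward ferric citrate. That needs a chain of events: onset in the first week, upset persisting after the reduction, withdrawal before day 14, no usable close-out sample, and a smaller rise than in those retained. Close-out blood is requested from everyone withdrawn early, and one sample counted as post-baseline keeps the participant in. Section 3.9.2 records adverse events at follow-up visits, the first at week 2, so acting on the steps earlier needs unscheduled contact. As the two-arm figures show, the net shift can also go the other way.

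These objections stand against any claim of a demonstrated bias or a known size. It is also fair that Section 4.3 prints its inclusion rule in full, so nothing is concealed.

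Three things remain. The close-out sample is requested, not assured, and Section 4.3 does not say whether it counts or at which time point. Section 3.6 expects participants to report missed doses between visits, so contact before week 2 is foreseeable. Exits on request are open to both arms, but they do not cancel a difference built into one protocol-defined route.

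**Conclusion.** The point holds in a limited form. The set is modified ITT under an intention-to-treat label. Taken alone, the gastrointestinal steps can precede the week-2 sample only in the ferric citrate arm. Where no close-out sample is obtained, exclusions may therefore differ by arm, and they could favour ferric citrate if those excluded gained less iron.

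The direction is possible, not shown, and the size cannot be derived without a dropout rate. Against a target difference of 15.5 ng/ml, the one-arm illustration for 1 to 3 exclusions runs from 2.6 to 7.8 at the unfavourable end (no rise in those excluded, no ferrous sulfate losses, no close-out samples), through zero, to negative values. The upper figures should not be read as an estimate.

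Separately, Section 3.7.1 keeps those who stop study drug in follow-up, while Section 3.9.1.1 withdraws participants with persistent upset from the study. These sections must be reconciled, because whether such a participant provides later data depends on which one staff follow.

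**What to change.** 1. Define the primary efficacy set as all randomised participants in their assigned arm. Drop the one-dose condition, so that never-dosed participants with follow-up values are included.
2. State that close-out samples count as post-baseline assessments, and at which time point they enter the mixed model.
3. Rename the present set modified ITT and use it as supportive.
4. Add a missing-data sensitivity analysis for participants with no post-baseline value, for example no change from baseline, with the assumed change varied by arm. Report exclusions by arm and reason.
5. Reconcile Sections 3.7.1 and 3.9.1.1 on follow-up of participants with persistent gastrointestinal upset. This review takes no view on which clinical rule should stand.

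The cost is SAP wording and one extra analysis run, with no change to the sample size. The effect estimate may be slightly smaller.
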